3.8 INTERIM ANALYSES

There is no interim analysis planned as part of this study.

A primary database lock will be performed when all randomized participants have completed or discontinued their treatment phase. Final analyses in the CSR will be based on all data collected up to this database lock.

[figure not shown]
The database will be updated at the end of the study for all participants to include the posttreatment follow-up information and updates for the events previously ongoing at the time of the primary lock. Additional data between this database lock and last participant completing last visit will be summarized in a CSR addendum.

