Any abnormal laboratory value will be immediately rechecked for confirmation within a reasonable timeframe as assessed by the Investigator before making a decision of definitive discontinuation of the IMP for the concerned participant.

Handling of participants after definitive intervention discontinuation

If participants no longer wish to take the IMP, they will be encouraged to remain in the study.

The Investigators should discuss with them key visits to attend. The value of all their study data collected during their continued involvement will be emphasized as important to the public health value of the study.

Participants who withdraw from the study intervention should be explicitly asked about the contribution of possible AEs to their decision, and any AE information elicited must be documented.

Participants will be followed-up according to the study procedures specified in this protocol up to the scheduled date of study completion, or up to recovery or stabilization of any AE to be followed-up as specified in this protocol, whichever comes last.

Participants who discontinue the study intervention prematurely (prior to completing the 52-week treatment period) will perform, as soon as possible, the early termination visit with all assessments normally planned for the end of treatment (EOT) Visit (Visit 7) (refer [Section 8.1.1](#)) including a pharmacokinetics sample, if appropriate, to assure a complete clinical assessment in close temporal proximity to the premature termination of study treatment is available.

In addition, and to allow assessment of participant outcomes over the stipulated study period, participants will be asked and encouraged to complete all remaining study treatment visits, and participate in all assessments according to the visit schedule with a ± 3 day window. Under exceptional circumstances when a participant cannot come to the site for a scheduled visit, a phone contact can be made. During the phone contact, at least information about AEs, concomitant medication, and status of AFRS should be collected.

All cases of definitive intervention discontinuation must be recorded by the Investigator in the appropriate pages of the eCRF when considered as confirmed.

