9.5 INTERIM ANALYSES

There is no interim analysis planned as part of this study.

A primary database lock will be performed when all randomized participants have completed their treatment phase. Final analyses in the CSR will be based on all data collected up to this database lock.

The database will be updated at the end of the study for all participants to include the posttreatment follow-up information and updates for the events previously ongoing at the time of the primary lock. Additional data between this database lock and last participant completing last visit will be summarized in a CSR addendum.

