3.2.2 Main analytical approach

The primary endpoint will be analyzed with the estimand defined according to the following attributes:

- Endpoint: Change from baseline in LMK score at Week 52
- Treatment condition: dupilumab will be compared to placebo
- Analysis population: ITT population
- Intercurrent events (IE):
 - The following intercurrent events will be handled with a composite strategy; data after the IE will be excluded and the worst post-baseline value on or before the start of the IE will be assigned to the Week 52 value (WOCF); for participants with no post-baseline values, the baseline value will be used.
 - Undergo/plan to undergo surgery for AFRS prior to Week 52
 - Taking SCS for any reason prior to Week 52

- The following IEs will be handled with the treatment policy strategy (without IEs that need to be handled with composite strategy). All assessments after starting such IE will be included.
 - Discontinuing the study intervention
 - Taking antifungals or other prohibited/rescue medications
- Population-level summary:

The primary endpoint will be analyzed using an analysis of covariance (ANCOVA) model with the baseline LMK score, intervention group, time from last surgery (≤ 2 years, >2 years), and region (Americas: Argentina, USA, Canada; Asia: China, Japan, India, Turkey, Saudi Arabia) as covariates, with intercurrent event strategies and missing data handling as defined in [Table 3](#).

Data of participants who undergo/plan to undergo surgery for AFRS or take SCS for any reason on or before Week 52 will be excluded from analysis after the IE, and the worst postbaseline value on or before the start of IE will be used to assign missing endpoint value (for participants whose postbaseline values are all missing, the baseline will be used to impute). Participants who discontinue the intervention prematurely are encouraged to follow the planned clinical visits and in those participants who did not have any of the above IE, all data collected after intervention discontinuation will be used in the analysis. For these participants, missing data may still happen despite all efforts to collect the data after treatment discontinuation. A multiple imputation (MI) approach will be used to impute missing endpoint value, and this MI method will use all participants excluding participants with the above IE. The imputation number will be 40.

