3.3.1.2 Main analytical approach

Continuous secondary efficacy endpoints

Continuous secondary efficacy endpoints will be analyzed similarly as primary estimand of primary endpoint.

[figure not shown]
Percent change from baseline in total IgE in serum at Week 52

[figure not shown]
This secondary endpoint will be analyzed similarly as primary estimand of primary endpoint, and will be performed on safety population.

[figure not shown]
Proportion of participants who receive SCS and/or undergo/plan to undergo surgery for AFRS during the planned study treatment period

[figure not shown]
This secondary endpoint will be analyzed with the primary estimand defined according to the following attributes:

[figure not shown]
- Endpoint: Proportion of participants who receive SCS and/or undergo/plan to undergo surgery for AFRS during the planned study treatment period
- Treatment condition: dupilumab will be compared to placebo
- Analysis population: ITT population
- Intercurrent events (IE):
 - The following IEs will be handled with a treatment policy strategy:
 - Discontinuation of study intervention
 - Taking antifungals or other prohibited/rescue medications
- Population-level summary
 - After the implementation of IE handling strategy,
 - Missing data handling: Participant who discontinue the study prior to Week 52 without an event will be considered as no event.
 - Risk difference between interventions as well as the corresponding 95% confidence interval (CI) will be estimated using Mantel-Haenszel estimate and confidence limits, with Mantel-Haenszel stratum weights for time from last surgery (≤ 2 years, > 2 years) and region (Americas, Asia) and the Sato variance estimator. The P-value associated with Mantel-Haenszel method will be provided.
 - Descriptive statistics including number and proportion of participants with events will be provided for each intervention group.

[figure not shown]

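### SAP 3.8 lets the primary lock precede the Week 52 visit of late-randomised participants who stopped treatment but are still followed; few are exposed, and most lose no Week 52 LMK value

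*SAP*

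**What the plan says.** - **Lock trigger, SAP 3.8:** "A primary database lock will be performed when all randomized participants have completed or discontinued their treatment phase".
- **Data used, SAP 3.8:** "Final analyses in the CSR will be based on all data collected up to this database lock". What arrives later is covered by: "Additional data between this database lock and last participant completing last visit will be summarized in a CSR addendum". Nothing says that the primary analysis is rerun.
- **Lock trigger, Protocol 9.5:** the lock comes "when all randomized participants have completed their treatment phase". Discontinuation is not mentioned. The SAP's table of modifications lists three departures from the protocol's statistical section (pandemic summaries, prohibited biologics, risk difference in place of odds ratio). The lock trigger is not among them.
- **Estimand, SAP 3.2.2:** for participants who stop treatment without surgery for AFRS or systemic corticosteroids (SCS), "all data collected after intervention discontinuation will be used in the analysis".
- **Follow-up, Protocol 7.1.1:** after stopping drug, "participants will be asked and encouraged to complete all remaining study treatment visits".
- **Rescue endpoint, SAP 3.3.1.2:** "Participant who discontinue the study prior to Week 52 without an event will be considered as no event".

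**The concern.** The estimand needs Week 52 data from people who stop drug early, and the protocol tries to collect them. The SAP trigger can be met by someone who has stopped drug and is still attending visits. If the last participants randomised are such people, the lock can come before their Week 52 visit.

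For example, suppose the last participant stops early and the one before, randomised 4 weeks sooner, completes. The trigger is then met 4 weeks before the last Week 52 visit is due. The resulting gap would be created by the plan, would fall only on treatment discontinuers, and would be avoidable.

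**Working it through.** The plan gives no figure to reproduce. The check compares the wording, then sizes the exposure.

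**1. Meaning of the trigger.** Neither document defines the treatment phase. Protocol 4.4 describes a person who discontinues the treatment period before Week 40 and is still followed to Week 52. SAP Appendix 2 pairs non-completion of the treatment period with permanent intervention discontinuation and counts study discontinuation separately. Both link discontinuing treatment to stopping drug.

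**2. Who is exposed.** The trigger date is the latest of the completers' Week 52 dates and the discontinuers' stop dates. A discontinuer randomised before the last-randomised completer reaches Week 52 before that completer does, so before the trigger. Only discontinuers randomised after the last-randomised completer can be cut off.

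**3. How many.** Let p be the discontinuation rate, which the documents do not give (assumed 5% to 30%).
- At least one person is exposed if the last participant randomised is a discontinuer: probability p.
- At least k are exposed only if the last k are all discontinuers: probability at most p^k.
- Mean number exposed: at most p + p² + … = p/(1 − p).

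A simulation of 20,000 trials of 62 agrees to within simulation error. It assumed uniform accrual over 24 or 36 months, uniform stopping on days 1 to 364, and that every discontinuer stays in follow-up.

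| p | p/(1 − p) | p³ (bound for 3 or more) | Simulated P(≥1), 24 / 36 months | Simulated mean, 24 / 36 months |
|---|---|---|---|---|
| 5% | 0.053 | 0.0001 | 5.1% / 5.1% | 0.053 / 0.053 |
| 10% | 0.111 | 0.001 | 10.2% / 9.8% | 0.114 / 0.108 |
| 20% | 0.250 | 0.008 | 20.0% / 20.7% | 0.247 / 0.255 |
| 30% | 0.429 | 0.027 | 30.0% / 29.4% | 0.420 / 0.407 |

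Three or more exposed has probability below 3% throughout, so 0 to 2 of 62 is the likely range. When anyone is exposed, the trigger precedes the last Week 52 date by about 11 to 22 days on average.

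**4. Can a Week 52 LMK value be lost?** Protocol 8.1.1.1 allows at most three CT scans, asks for one at premature discontinuation, and does not require the Week 24 scan in adolescents/children.

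| Participant | Scans used before Week 52 | Week 52 scan possible? |
|---|---|---|
| Adult, stops before Week 24 | Screening, early termination, Week 24 = 3 | No |
| Adult, stops after Week 24 | Screening, Week 24, early termination = 3 | No |
| Adult, Week 24 scan not done or same as early termination | 2 | Yes |
| Adolescent/child | Screening, early termination = 2 | Yes |

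SAP Table 7 assigns any CT after day 266 to Week 52. So even in the last two rows a value is lost only if the early-termination CT was on or before day 266. Applying the day-266 rule alone, the simulated chance that at least one LMK value is lost was about 4% (p = 5%) to 23–24% (p = 30%). The scan cap was not applied, so these are upper limits under the same assumptions.

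**5. What else can be lost.**
- *Nasal polyp score (NPS), SNOT-22 and diary.* No scan cap applies. Table 7 places NPS and SNOT-22 from days 308 to 405 at Week 52, and Table 8 uses diary days 338 to 365. Early-termination visits before day 308 do not supply the first two. NPS, nasal congestion and SNOT-22 at Week 52 are in the SAP 3.5 testing hierarchy.
- *SCS or AFRS surgery between lock and Week 52.* These are events for the rescue endpoint, also in the hierarchy. They also decide whether LMK is set by worst observation carried forward (WOCF) or left to the observed value or multiple imputation. This applies even when no further CT is possible.

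**6. Weight.** Each affected participant is 1/31 = 3.2% of an arm. The text available gives no LMK difference or SD, so the stated power above 99% cannot be checked. Taking exactly 99% with 31 per arm implies a standardised difference of (1.960 + 2.326) × √(2/31) = 1.089. At that difference, 30, 29 and 28 per arm give 98.8%, 98.6% and 98.3%.

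**The case against.** The case for leaving the text alone has real force.

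- **The wording is ambiguous.** The treatment phase is undefined, Protocol 7.1.1 places off-drug participants within the remaining treatment visits, and SAP 3.8 describes the later update as post-treatment follow-up and ongoing events. The protocol sentence, read strictly, could never be met once anyone withdrew, so the added words may be a repair. This stands as a plausible intention. It does not settle the matter, because Protocol 4.4 and SAP Appendix 2 use the terms the other way and no passage makes the lock wait for Week 52.
- **Trigger and lock are different dates.** Analyses use data up to the actual lock. Any interval between the two, which the documents do not give, shortens the gap. This stands.
- **LMK is largely protected.** A reader might infer that the rule generally replaces obtainable primary-endpoint scans with imputed values. The documents do not support that: most adult discontinuers on schedule have no scan left for Week 52, a CT after day 266 already counts, and SCS or surgery before the lock fixes the value by WOCF.
- **The rescue rule is not stated for this case.** A reader might infer that someone still in follow-up at lock is counted as having no event. That rule is written for people who leave the study. How a participant still being followed would be counted is not stated.

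**Conclusion.** The point holds in limited form and is minor. On its literal wording, SAP 3.8 permits a lock before the Week 52 visit of late-randomised participants who stopped drug but are still followed. That conflicts with the treatment-policy strategy, and the wording differs from Protocol 9.5 without being listed as a change.

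The likely number exposed is 0 to 2 of 62. This rests on assumed discontinuation rates, accrual and stopping patterns, and on every discontinuer staying in follow-up. The main loss is Week 52 NPS, SNOT-22 and diary data, and SCS or surgery events that affect the rescue endpoint and the handling of LMK. Direct loss of an LMK value is confined to those with a third scan still available and an early-termination CT on or before day 266. The issue is avoidable missing data and fidelity to the estimand; the effect on power is trivial.

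**What to change.** Reword the SAP 3.8 trigger so that the primary lock takes place *once every randomised participant has completed the Week 52 visit (on or off treatment) or has withdrawn from the study*. Align Protocol 9.5, and add the change to the SAP's table of modifications.

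Withdrawals would still not block the lock, and no participant in follow-up would lose Week 52 data because of it. The cost is one phrase and a possible delay of a few weeks, incurred only if the last participants randomised stopped drug early.

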3.9 CHANGES TO PROTOCOL-PLANNED ANALYSES

This section summarizes major statistical changes in the protocol amendment(s).

Major statistical changes in protocol amendment(s)

Amendment Number	Approval Date	Changes	Rationale
3	01-Mar-2023	
The sample size changed from 120 (60 per arm) to 62 (31 per arm). The updated study power is >99% for the primary endpoint and 80% for the secondary endpoint using an alpha=0.05.
 
Updated text to reflect switching of primary to secondary endpoint and vice-versa.
 
In statistical considerations, 1) primary and secondary endpoint switched, 2) stratification factor of disease pattern removed from the statistical model, and 3) intercurrent event of taking SCS for any reason changed from treatment policy to composite strategy (WOCF).
 
Alpha level of 0.01 was changed to 0.05 and study is considered positive when the primary endpoint achieves statistical significant with 2-sided significance level 0.05.
	
A sample size of 62 participants would provide ample power for the new primary endpoint based on change from baseline in LMK at Week 52, which is a clinically relevant measure of efficacy. The new sample size would allow for sufficient power for the original primary endpoint of rescue therapy utilization as a secondary endpoint.
 
The primary and secondary endpoints were switched, and the sample size was optimized based on this change. The stratification factor for disease pattern was removed from the statistical model due to only rare unilateral participants identified. The treatment policy was changed to composite strategy, an approach more appropriate for this clinical setting.
 
The alpha level was adjusted to support an optimized sample size for this rare condition.

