1.1 Synopsis, 3 Objectives and Endpoints, 9.4.3 Secondary endpoint(s)		
1.1 Synopsis, 4.1 Overall Design	Added text for stratification by time from last surgery to include 'surgery naïve participants' for those in ' ≤ 2 years' group	To align with the removal of inclusion criterion I04.
1.1 Synopsis, 4.1 Overall Design, 3.1 Appropriateness of Measurements, 9.2 Sample size determination	
The sample size changed from 120 (60 per arm) to 62 (31 per arm).
 
The updated study power is $>99\%$ for the primary endpoint and 80% for the secondary endpoint using an alpha=0.05.
	A sample size of 62 participants would provide ample power for the new primary endpoint based on change from baseline in LMK at Week 52, which is a clinically relevant measure of efficacy. The new sample size would allow for sufficient power for the original primary endpoint of rescue therapy utilization as a secondary endpoint.
1.1 Synopsis, 9.4.2 Primary endpoint(s), 9.4.3 Secondary endpoint(s)	Updated text to reflect switching of primary to secondary endpoint and vice-versa.	
	In statistical considerations, 1) primary and secondary endpoint switched, 2) stratification factor of disease pattern removed from the statistical model, and 3) intercurrent event of taking SCS for any reason changed from treatment policy to composite strategy (WOCF).	The primary and secondary endpoints were switched, and the sample size was optimized based on this change. The stratification factor for disease pattern was removed from the statistical model due to only rare unilateral participants identified. The treatment policy was changed to composite strategy, an approach more appropriate for this clinical setting.

Section # and Name	Description of Change	Brief Rationale
1.2 Schema	Schema updated with updated number of participants in each study arm	To reflect the change in sample size
1.3 Schedule of Activities (SoA)	Updated Footnote 'c' to add more clarity in study completion definition. Added below text to Footnote 'j' Questionnaires in paper form are not permitted; only electronic form is allowed.	Clarification of study completion date to align with Section 4.4. Clarification that paper documentation is not permitted.
	Added below text to Footnote 'm' Physician assessment UPSIT may not be available at some sites for visits; in this case the Investigator may omit the test for that visit.	To add flexibility for UPSIT assessment due to variable availability of testing materials at sites.

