4 STUDY DESIGN

4.1 OVERALL DESIGN

This is a Phase 3, multicenter, 52-week treatment, parallel-group, double-blind, randomized, placebo-controlled study to investigate the efficacy of dupilumab 300 mg q2w for adults and adolescents/children (≥ 6 to < 12 years) ≥ 60 kg, or dupilumab 200 mg q2w for adolescents/children ≥ 30 kg and < 60 kg, dupilumab 300 mg q4w for adolescents/children ≥ 15 kg and < 30 kg with signs and symptoms of AFRS. The study will primarily investigate the efficacy of dupilumab to reduce disease burden in the sinuses (sinus opacification) by radiographic imaging. In addition, the study will also evaluate efficacy of dupilumab to reduce the need for repeated SCS and/or surgery, nasal polyps burden, clinical symptoms, and explore other measures of disease activity.

Approximately 62 participants (31 per arm) with AFRS who satisfy the inclusion and exclusion criteria will be randomized in a 1:1 ratio to receive either dupilumab or matching placebo:

- Dupilumab 300 mg q2w for all adults, 300 mg q2w for adolescents/children ≥ 60 kg at screening, or 200 mg q2w for adolescents/children ≥ 30 kg and < 60 kg at screening, or 300 mg q4w for adolescents/children ≥ 15 kg and < 30 kg at screening.
- Matched placebo.

Randomization will be stratified first by age (adults versus adolescents/children [≥ 6 years old]). In adults, randomization will be stratified further by time from last surgery (≤ 2 years [including surgery naive participants], > 2 years), disease pattern (unilateral/bilateral in the endoscopy at screening), and country. In adolescents/children, randomization will not be stratified further.

Duration of study period (per participant):

- Screening period (2 to 4 weeks): to determine a participant's eligibility and continue with his/her own background intranasal corticosteroids (INCS) prior to randomization.
- Randomized IMP intervention period (52 weeks ± 3 days): to randomize the participants into a treatment arm and treat with dupilumab or placebo dose regimen.
- Follow-up period (12 weeks ± 5 days): to continue to collect data for PK, immunogenicity, safety, and efficacy after the participant has completed the randomized IMP intervention period.

The total duration of study participation for participants that complete the randomized treatment period and posttreatment follow-up is approximately 68 weeks. The schedule of the visits is described in the specific flow-chart in [Section 1.3](#).

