3.5 MULTIPLICITY ISSUES

The multiplicity procedure is proposed to control the overall type-I error rate for testing the primary and selected secondary endpoints. The overall alpha is 0.05. The comparisons with placebo will be tested based on the hierarchical order below at 2-sided $\alpha = 0.05$:

- Change from baseline in sinus opacifications assessed by CT scans using LMK score at Week 52
- Change from baseline in monthly average nasal congestion/obstruction score from the Nasal Symptom Diary at Week 24
- Change from baseline in endoscopy NPS at Week 24
- Change from baseline in sinus opacifications assessed by CT scans using LMK score at Week 24
- Change from baseline in monthly average TSS derived from the Nasal Symptom Diary at Week 24
- Change from baseline in UPSIT at Week 24
- Change from baseline in the score of decreased/loss of smell using the Nasal Symptom Diary at Week 24
- Change from baseline in endoscopy NPS at Week 52
- Change from baseline in monthly average nasal congestion/obstruction score from the Nasal Symptom Diary at Week 52
- Change from baseline in SNOT-22 total score at Week 52
- Change from baseline to Week 52 in three-dimensional CT total volume occupied by disease in all sinuses (%)
- Proportion of participants who receive SCS and/or undergo/plan to undergo surgery for AFRS during the planned study treatment period
- Change from baseline in SNOT-22 total score at Week 24
- Percent change from baseline in total IgE in serum at Week 52

The study is considered positive when the primary endpoint achieves statistical significance with 2-sided significance level 0.05.

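### Does testing the rescue endpoint 12th of 14 contradict the 80% power stated for it?

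*SAP*

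**What the plan says.** SAP 3.9 records the cut from 120 to 62 participants (31 per arm) and gives the resulting power: "The updated study power is >99% for the primary endpoint and 80% for the secondary endpoint using an alpha=0.05". The adjoining rationale identifies the secondary endpoint: "The new sample size would allow for sufficient power for the original primary endpoint of rescue therapy utilization as a secondary endpoint". The summary of changes in the Protocol (Amendment 03, dated 01-Mar-2023) says the same.

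Protocol 9.4.1 leaves the detailed testing order to the SAP, which was approved on 22-Jan-2025. SAP 3.5 sets it: "The comparisons with placebo will be tested based on the hierarchical order below at 2-sided" 0.05, with the added statement "The overall alpha is 0.05". Fourteen endpoints are listed. Number 12 is "Proportion of participants who receive SCS and/or undergo/plan to undergo surgery for AFRS during the planned study treatment period". Ahead of it, in order, stand:

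1. LMK at Week 52 (the primary)
2. Congestion at Week 24
3. NPS at Week 24
4. LMK at Week 24
5. TSS at Week 24
6. UPSIT at Week 24
7. Diary loss of smell at Week 24
8. NPS at Week 52
9. Congestion at Week 52
10. SNOT-22 at Week 52
11. Three-dimensional CT disease volume at Week 52

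Only the first of these eleven has a stated power. For UPSIT, the entry on Schedule of Activities footnote m in the Protocol's summary of changes says: "UPSIT may not be available at some sites for visits; in this case the Investigator may omit the test for that visit".

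**The concern.** Someone who reads 80% power in SAP 3.9 may take it as the chance of a valid positive claim on rescue under this plan. In a fixed sequence that claim requires tests 1 to 12 all to be significant, so a miss on any one of eleven tests blocks it. One of the eleven is a smell test that sites may skip when kits are unavailable. Rescue was the primary endpoint before Amendment 03, and Protocol 3.1 treats the need for steroids or surgery as an important part of disease burden. If 62 participants are defended partly by the power for rescue, and the SAP then places rescue near the bottom of the list, the stated power seems to promise more than the testing procedure can deliver. At stake would be the confirmatory status of the rescue result.

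**Working it through.** **Inputs from the documents.** 31 per arm, 1:1; two-sided 0.05 at each step; power above 99% for test 1 and 80% for rescue; rescue at position 12. The rescue rates, the LMK effect and SD, the power of tests 2 to 11 and the correlations are not in the text available for this review. Protocol 9.2, on sample size, is named there but its text is not included, and that is not a fault of the plan.

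**Is 80% plausible as a stand-alone figure?** It cannot be reproduced without the rates, but it can be checked for attainability. For a pooled two-sided test of proportions with 31 per arm, take assumed rates of 50% on placebo and 17% on dupilumab. The mean rate is 0.335, and

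z = (√31 × 0.33 − 1.96 × √(2 × 0.335 × 0.665)) / √(0.5 × 0.5 + 0.17 × 0.83) = (1.837 − 1.308) / 0.625 = 0.85, so power is about 80%.

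Other pairs that give 80% are 30%/3.8%, 40%/9.8%, 60%/25.5% and 70%/35.1%. The figure is attainable with differences of 26 to 35 points and is not shown to be wrong.

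**Direction.** Let A be the event that tests 1 to 11 succeed and B that rescue succeeds. Then P(A and B) = P(B) × P(A given B) ≤ 0.80. Equality needs only that the earlier tests succeed whenever rescue does. They need not be certain in themselves: with perfect dependence and ten gates of only 80% power each, the gated power is still 80.0%. The loss comes from gating alone, because step 12 keeps the full 0.05.

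**Size, under assumptions.** Set test 1 at 99%, rescue at 80% marginal, and a common assumed power g for tests 2 to 11. Under independence the gated power is 0.99 × g^10 × 0.80; for g = 0.95 that is 0.99 × 0.5987 × 0.80 = 47.4%. With equicorrelated normal test statistics (400,000 simulated trials) it is:

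| g for each of tests 2–11 | ρ = 0 | ρ = 0.3 | ρ = 0.5 | ρ = 0.7 | ρ = 0.9 |
|---|---|---|---|---|---|
| 80% | 8.5% | 25.5% | 36.9% | 49.0% | 63.8% |
| 90% | 27.6% | 45.0% | 54.9% | 64.8% | 75.5% |
| 95% | 47.4% | 59.7% | 66.8% | 73.3% | 79.3% |
| 99% | 71.6% | 75.0% | 77.3% | 79.2% | 79.9% |

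The ρ = 0 column is not credible here. TSS is built from congestion, smell and rhinorrhea (SAP 3.3.1.1). LMK and the three-dimensional volume use the same CT acquisitions (Protocol 8.1.1). LMK, NPS and congestion each appear twice among the eleven. SCS use or surgery, the rescue event itself, also triggers worst-observation carry-forward in the continuous endpoints (SAP Table 2), which ties the gates to rescue. Neither the true correlation nor the true g can be read from the documents.

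**Would reordering help?** Take g = 90% and independence, the case where gating costs most.

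- UPSIT moved to the end: 0.99 × 0.9^9 × 0.80 = 30.7%, against 27.6%. At ρ = 0.5 the change is from about 55% to 56.3%.
- Rescue moved ahead of UPSIT, to 6th: 0.99 × 0.9^4 × 0.80 = 52.0%. The price falls on what follows: a controlled UPSIT claim drops from 0.99 × 0.9^5 = 58.5% to 58.5% × 0.80 = 46.8%, and every later endpoint carries the same factor.

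**The case for a change.** The strongest case for a change is this. The direction of the effect needs no assumption. The SAP fixed the order and repeated the 80% in the same document without saying that it is marginal, and only one of the eleven gates has a stated power. There are also reasons not to treat the gates as near certain: the Week 24 CT is not required for adolescents or children, the diary, SNOT-22 and UPSIT are not collected under age 12, and UPSIT may be omitted. Even at correlation 0.7, gates at 90% leave about 65%. At the standardized LMK difference that gives 99% power with 31 per arm, (1.960 + 2.326) × √(2/31) = 1.09, the primary alone would need 2 × (1.960 + 1.282)² / 1.09² ≈ 18 per arm for 90% power. That suggests rescue had a hand in the choice of 62.

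What stands is that 80% is a ceiling for a controlled claim and that a label would spare the reader the inference. The rest is weaker. The wording, power at an alpha of 0.05, is the usual way to report a single test, and it dates from an amendment made before the order existed. That rescue set the sample size is inference: the stated rationale first cites ample power for LMK and then adds rescue. Missing values in continuous secondary endpoints are multiply imputed, so an omitted UPSIT costs precision but does not stop the test.

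**Conclusion.** No change to the plan is needed. The 80% is a marginal power at two-sided 0.05; a statistician would read it that way, and nothing in the documents claims it for the gated test. The power for a controlled rescue claim is at most 80%, and lower unless the eleven earlier tests almost always succeed when rescue does. The shortfall ranges from under 1 point (gates at 99%, correlation 0.7) to about 15 points (gates at 90%, correlation 0.7), and more with weaker or less correlated gates; all of these rest on assumed gate powers and correlations.

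Following the SAP as written controls type I error across the sequence, leaves the primary conclusion untouched, and still reports the rescue risk difference with its confidence interval and p-value (SAP 3.3.1.2). Only the confirmatory status of rescue depends on its rank. That rank is a clinical ordering by the sponsor, which moved rescue out of the primary position because of pandemic effects on it. Raising it would put other secondary endpoints at risk in its place, and moving UPSIT to the end gains almost nothing.
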